At triage, patients will be advised that they will be tested for HIV and/or HCV unless they refuse to be tested or are already known to be infected with HIV and/or HCV. If a patient is known to be infected with HIV or HCV, they may be tested for the virus whose status is unknown. The time required to educate the patient and obtain answers to questions will be measured for a sample of patients after an initial period of staff adjustment. The nurse performing the collection will be the same nurse who performs the patient's regular blood work. She will use the pre-printed orders for this purpose. The physician in charge of receiving the results will be one of the study investigators. Patients who do not have to have their blood drawn for their health problem will still be offered the test.

Results management:

Patients will be notified that they will receive their test results without specifying how. As opposed to having all patients travel or announcing all results over the phone, this strategy is intended to ensure that patients called back for an appointment do not spontaneously understand that they are infected with HIV or hepatitis C when they are home alone, while limiting the number of patients who will have to travel since the vast majority of tests will be negative.

The research nurse will have access to the results of all tests performed via the CHUM computer system. In the event of a positive result (confirmed by the Laboratoire de santé publique du Québec (LSPQ) for HIV and by the CHUM laboratory +/- the LSPQ as needed for HCV), she will notify one of the investigators who will contact the patient in person, if he or she is still present at the hospital, or by giving him or her an appointment, if he or she has left. The research nurse will organize a follow-up with one of the CHUM's specialized clinic coordinators, taking into account the diagnosis, the type of clientele and the person's choice. The time required to reach the patient and plan the liaison with the care team as well as the mode of communication used will be noted. If the result is negative, the physician will delegate the research nurse to contact the patient to give him or her the result, either by telephone or by mail, depending on the method of communication available in the hospital file.

Health system linkage:

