The research nurse will check the hospital's computer system to see if the patient has been seen in a specialty clinic within one month of the positive test announcement. If not, the research nurse will follow up with the patient by phone to see if they have been seen outside the hospital for this new diagnosis. If after three attempts to call, the patient is not reached, they will be considered not linked to the health care system. For HIV patients, she will check for confirmatory

serology, viral load, and CD4 count and whether treatment has been initiated. For HCV, she will verify that RNA testing and, if applicable, genotyping have been performed. For chronic HCV patients, she will assess at 3 months whether liver fibrosis has been assessed and whether treatment has been prescribed.

Eligibility criteria for the cross-sectional HIV/HCV screening component of the study:

Inclusion criteria :

Individuals between the ages of 18 and 73 years consulting the CHUM emergency department regardless of the time of consultation.

Exclusion criteria :

Persons unable to refuse the test, notably because of their medical condition leading them to consult the emergency room.

If the person's condition improves during the emergency room visit, they may be offered screening at that time.

Eligibility criteria for the linkage-to-care of HIV/HCV-infected patients component of the study:

Inclusion criteria:

- Patient who has agreed to HIV or HCV test(s) in the UHC emergency department.
- Aged 18 years to 73 years
- Tested positive for HIV and/or HCV
- Able to consent and sign the information and consent form

Outcomes:

Primary outcomes

1. Prevalence of unknown HIV or HCV infections in the CHUM emergency department during the study period: positive tests / tests performed in unknown patients with HIV or HCV
2. Overall prevalence of HCV and HIV during the study period: (positive tests + known positive cases) / (tests performed + known positive cases)

Secondary outcomes

1. For HCV, among baby boomers (1945-1975 or 43-73 years)
 - a. Prevalence of new cases (positive tests/tests performed)
 - b. Overall prevalence (positive tests + known positive cases) / (tests performed + known positive cases)
2. Staff adherence: (tests performed, refused or known positive) / (eligible patients)
3. Proportion of patient opt-outs: tests refused / (tests performed + tests refused)

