The sample size was based on the threshold prevalence of newly diagnosed HIV infection that warrants the implementation of a routine HIV testing program (1/1000 according to the CDC). Assuming a prevalence of undiagnosed cases of 1/1000, a study of 4,000 subjects would yield a 95% confidence interval of 0.3/1000 to 2.7/1000. For HCV, assuming a prevalence of undiagnosed cases of 1/100, we will obtain a 95% confidence interval between 0.7 and 1.3%. In 2014-2015, 110 420 consultations took place in the CHUM emergency department.²⁰ Patients were between 18 and 74 years of age in 85% of cases,²⁰ which represented 93 857 consultations per year (7821/month). Few studies have reported missed opportunities for screening in emergency department opt-out situations. One study reported 49.9% missed opportunities due to either staff oversight or patient refusal.¹¹ In other studies, patient refusal rates were in the range of 30-35%.^{8,9} Assuming a proportion of patient refusal and staff oversight of 50%, the recruitment period should be a maximum of 2 months.

Analyses

Descriptive statistics with 95% confidence intervals will be used to calculate, separately for HIV and HCV, the prevalences of new and known cases and the proportions of "opt-out" and staff adherence to testing. The prevalences of new and known HCV cases among baby boomers will be calculated in the same way. Medians and their confidence intervals will be calculated for the time required to inform the patient of the screening and for the time required to announce the result. Program costs will be presented in absolute terms and as a cost per newly diagnosed case. Liaison with a specialized team, completion of the initial workup and initiation of treatment at one month (HIV) or three months (HCV) will also be presented as proportions with their confidence intervals.

Ethical and Regulatory Considerations

Research Ethics Board

The protocol, forms and regulatory documents will be submitted to and approved by the CHUM Research Ethics Committee and Scientific Committee.

Information and consent form

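### The primary prevalences are built from tests and triage-reported known cases, with no rule limiting each person to one entry, although the objectives and the 4,000 subjects are people.

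*Combined protocol and SAP*

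**What the plan says.** In the combined protocol and SAP, the first item under Outcomes, Primary outcomes is the prevalence of unknown infection, calculated as "positive tests / tests performed in unknown patients with HIV or HCV". The second is "Overall prevalence of HCV and HIV during the study period: (positive tests + known positive cases) / (tests performed + known positive cases". The baby-boomer HCV outcomes repeat the same two ratios.

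Other sections speak of people. The primary objectives concern patients visiting the emergency department. Eligibility covers "Individuals between the ages of 18 and 73 years consulting the CHUM emergency department regardless of the time of consultation". The sample-size section states that "a study of 4,000 subjects would yield a 95% confidence interval of 0.3/1000 to 2.7/1000". Data collection says that the triage sheets will give the number of known patients for each virus.

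Accrual, however, is worked out from visits: the 18-to-74 share of annual volume, "which represented 93 857 consultations per year (7821/month" in the text, followed by "Assuming a proportion of patient refusal and staff oversight of 50%, the recruitment period should be a maximum of 2 months".

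Under Screening, patients are told they will be tested "unless they refuse to be tested or are already known to be infected with HIV and/or HCV". A previous study test is not among the exceptions. Under Analyses, "Descriptive statistics with 95% confidence intervals will be used to calculate, separately for HIV and HCV, the prevalences of new and known cases". No step reduces the data to one record per person.

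**The concern.** The target is a proportion of people, while outcome 1 is a proportion of tests. A person who tests negative and comes back during the study period is still of unknown status, is not exempt under Screening, and adds a second test to the denominator of both outcomes without adding a person.

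Outcome 2 also depends on known cases identified on triage sheets, which are completed at visits. If whoever builds the data file counts triage entries, a known case who returns appears twice in numerator and denominator. A person diagnosed by the study who returns and reports the infection appears once as a positive test and once as a known case.

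The counting unit of both primary estimates, and of their 95% intervals, is therefore left to be settled when the data are assembled. The errors run in opposite directions, so a reader could not correct them afterwards without person-level counts.

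**Working it through.** **Plan's own figures.** Inputs from Sample size: 4,000 subjects, HIV 1/1,000, HCV 1/100.

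- HIV, 4/4,000: adding two successes and two failures gives 6/4,004, and 1.96 × √(p(1−p)/4,004) gives 0.30 to 2.70 per 1,000, as stated.
- HCV, 40/4,000: 1% ± 1.96 × √(0.01 × 0.99/4,000) = 0.69% to 1.31%, stated as 0.7% to 1.3%.
- Accrual: 110,420 × 0.85 = 93,857 a year; /12 = 7,821 a month; × 0.5 = 3,911 tests a month; 4,000/3,911 = 1.02 months, within the stated maximum of 2.

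These figures reproduce and are not in dispute.

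**Outcome 1, repeat negatives.** The share r of tests that are repeats is assumed. People tested = 4,000(1−r), with 4 HIV and 40 HCV positives.

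| r | People | HIV per 1,000 | HCV % |
|---|---|---|---|
| 0 | 4,000 | 1.00 | 1.00 |
| 2.5% | 3,900 | 1.03 | 1.03 |
| 5% | 3,800 | 1.05 | 1.05 |
| 10% | 3,600 | 1.11 | 1.11 |

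The test-based formula reports 1.00 in every row. The largest shift, 0.11, is 0.11/1.2 = 9% of the planned HIV half-width and 0.11/0.3 = 37% of the HCV one. Precision barely changes: 3,600 people at 1% give 0.67% to 1.33%.

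**Outcome 2, unequal numbers of entries.** Known cases are derived by applying the unaware shares in the rationale (HCV 44%, HIV 21%) to the planned new cases: 40 × 0.56/0.44 = 51 for HCV and 4 × 0.79/0.21 = 15 for HIV. With one entry each:

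- HCV: 91/4,051 = 2.25%, 95% half-width 0.46 points.
- HIV: 19/4,015 = 0.47%, half-width 0.21 points.

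Now let everyone else average 1.1 entries (assumed), with the extra 0.1 of new cases entered as known, and let known cases average m entries:

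- HCV = (51m + 44)/(4,400 + 51m)
- HIV = (15m + 4.4)/(4,400 + 15m)

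| m | HCV | HIV |
|---|---|---|
| 1.0 | 95/4,451 = 2.13% | 19.4/4,415 = 0.44% |
| 1.1 | 100.1/4,456.1 = 2.25% | 20.9/4,416.5 = 0.47% |
| 1.2 | 105.2/4,461.2 = 2.36% | 22.4/4,418 = 0.51% |

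Equal averages leave the estimate unchanged. The upward shift reaches the half-width only at about m = 1.5 (HCV) or m = 1.7 (HIV).

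**New positives re-entered as known, nobody else returning.** If 2, 4 or 8 of the 40 HCV cases return: 93/4,053 = 2.29%, 95/4,055 = 2.34%, 99/4,059 = 2.44%. If others return at the same rate, the shift disappears, as in the m = 1.1 row.

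**Accrual margin.** Two months at 50% yield 7,821 × 2 × 0.5 = 7,821 tests. Repeats would have to exceed 1 − 4,000/7,821 = 48.9% of tests before 4,000 distinct people were out of reach.

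**The case against.** The strongest reply is that people were plainly meant. The text speaks of patients, subjects and known patients, and elsewhere a case is someone who attends an appointment or starts treatment. On that reading, entering a known case twice, or a new positive again as known, departs from the text. This stands in part: double entry in outcome 2 is a risk if triage entries are treated as records, not the only literal meaning of the formula. It does not answer the retested negative, because the denominator is expressly tests performed.

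A reader might infer that both formulas are exposed to repeated known cases. They are not: outcome 1 has no known-case term, and its restriction to patients of unknown status removes a person once told of a positive result.

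A reader might also fear that one HIV-positive person tested twice would move the estimate to 5/4,001 = 1.25 per 1,000. That needs a return before the result is given, or non-disclosure at triage. Each confirmed positive is notified to an investigator and contacted individually, so this is unlikely to go unnoticed.

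It is also fair that the recruitment window is short, that consultations are used only to check feasibility, and that every size here is assumed. Nothing in the documents supports known cases averaging 1.5 or 2 entries while others average 1.1.

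**Conclusion.** The point holds as a modest correction that should be made. Outcome 1 is defined in tests where the objective concerns people, so retested negatives dilute it: 1.00 stands for 1.03 to 1.11 per 1,000 people at assumed repeat shares of 2.5% to 10%. Outcome 2 can move either way. It rises only if known or newly diagnosed people have more entries than others, for example HCV from 2.25% to 2.36% and HIV from 0.47% to 0.51% at 1.2 against 1.1 entries. These shifts lie inside the interval half-widths.

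The sizes rest on assumed return rates and on applying the Canadian HCV and Quebec HIV unaware shares to one emergency department. A reader might infer that the sample size, precision or two-month accrual is undermined; the arithmetic shows that it is not.

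**What to change.** Under Outcomes, define both primary prevalences and the baby-boomer versions per distinct person per virus, one entry each, linked by hospital file number:

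- Take the entry at the first study-period visit at which status is established: known positive if so reported then, otherwise the result of the person's first study test.
- Never count a person recorded as a new positive as known as well.
- Report separately a later positive after a negative study test, so that possible new infections do not enter a cross-sectional prevalence.
- Use distinct new cases for the cost per newly diagnosed case, and keep test counts for the volume and cost outcome (secondary outcome 6).

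The cost is a short paragraph and a de-duplication step. Test results already come from the hospital computer system. Triage answers would have to be linked by the same file number, and ethics cover for that linkage should be confirmed because screening proceeds without a consent form. The number of people will be slightly smaller than the number of tests. This is a counting rule only and does not say whether returning patients are offered another test.

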4. To determine the proportion of patients with a newly positive HIV or HCV test in the ED who attended a first appointment at 1 month
5. To determine the proportion who completed certain steps in the HIV and HCV care cascades at 1 or 3 months, namely confirmation of diagnosis (HIV and HCV: 1 month), liver fibrosis assessment (HCV: 3 months), and treatment initiation (HIV: 1 month and HCV: 3 months)
6. To define the organization of services needed to continue screening beyond the research project in terms of costs, nursing time, volume of tests and communication of results.

Design:

Cross-sectional study of ED patients with evaluation of the implementation of the screening program and prospective follow-up for 3 months of the positive cases.

Method:

Implementation: Preparatory meetings will be held with CHUM ED managers, medical leaders, and nurses to discuss issues associated with routine screening and to attempt to find solutions to anticipated barriers in advance. Following these discussions, ED triage staff, including day, evening and night staff, will be met for training on the importance of screening and the procedure that will be followed under this protocol.

Informational Tools:

Patient announcements

Information materials will be prepared to announce to CHUM ED patients that HIV and/or HCV testing will be performed. Posters will be put up in the ED and an information sheet will be given to patients at the time of registration.

Materials for Nurses:

The following items will be added to the triage form already in place in the ED: "Are you infected with HIV? Are you infected with HCV?", "Unless you decline, we will be performing a blood test for HIV (and/or) HCV today." These questions will simultaneously serve as a reminder for staff to offer the test and as a data collection form for investigators.

Pre-printed orders for HIV and HCV testing will also be created with the name and license number of one of the investigators.

Laboratory Tests:

The tests used will be the routine CHUM tests (ARCHITECT HIV Ag/Ab combo and ARCHITECT anti-HCV assay). These were chosen over rapid tests because

they are less expensive and more sensitive, they are more representative of what might be widely available in the event of a provincial rollout of ED screening, and there are no licensed rapid tests for HCV in Canada.

Screening:

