4. Linkage of positive cases to a care team 1 month post-test (definition: attended at least one appointment).
5. Progression through the care cascade at 1 and 3 months:

- a. HIV and HCV: confirmation of diagnosis and baseline laboratory testing at 1 month (HIV: confirmatory serology, viral load and genotyping; HCV: qualitative RNA measurement and genotyping)
 - b. HCV: liver fibrosis assessment at 3 months.
 - c. HIV and HCV: initiation of treatment for HIV at 1 month and HCV at 3 months.
6. Organization of services: nursing time to inform the patient, time for results management, mode of communication used to announce results, number of tests performed per period and associated costs.

Data collection

The number of eligible patients during the study period will be determined via data from the SIURGE system. Completed triage sheets will identify the number of known patients for each virus, the number of refusals, the number of patients not approached for the study and basic patient demographics (age, zip code).

The hospital computer system (OACIS) will be used to obtain the results of screening tests (including confirmatory tests performed at the LSPQ as part of an initial screening test) for all screened patients as well as management results for patients included in the cohort of infected patients (2nd confirmatory serology, viral load and genotyping for HIV, qualitative RNA, genotyping and liver fibrosis assessment for HCV). Management and initiation of treatment will be determined in OACIS or by follow-up calls 1 and 3 months after diagnosis depending on whether the patient has decided to be followed at the CHUM or not. The time required to notify patients of results will be recorded in the research nurse's observation sheets, as will the means of communication used to reach the patient. Test costs will be extracted from the Répertoire québécois et système de mesure des procédures de biologie médicale.¹⁹

Statistical Considerations

Sample size

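### Staff times are to be summarised only by medians, but judging the services needed for a volume of tests (secondary objective 6) also requires means or totals

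*Combined protocol and SAP*

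**What the plan says.** Secondary objective 6 is "To define the organization of services needed to continue screening beyond the research project in terms of costs, nursing time, volume of tests", followed by the communication of results. Secondary outcome 6 lists the matching measures, among them "nursing time to inform the patient, time for results management", together with test numbers per period and the associated costs.

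The Analyses section gives one sentence to the times: "Medians and their confidence intervals will be calculated for the time required to inform the patient of the screening". That sentence applies the same summary to announcing the result. No mean, sum or average time per patient is planned anywhere.

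Cost is handled separately: "Program costs will be presented in absolute terms and as a cost per newly diagnosed case". The only cost source named under Data collection concerns laboratory work: "Test costs will be extracted from the Répertoire québécois et système de mesure des procédures de biologie médicale". No wage, unit cost or rule connects recorded staff time to programme cost.

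Two details of data capture matter here.

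- Under Screening, the time to inform patients is to be measured in a sample of them only, after staff have had a period to adjust.
- Under Results management and Data collection, the time spent reaching and notifying patients is recorded by the research nurse. Negative results go out by telephone or mail. A positive result needs contact by an investigator, in person or by appointment, and the nurse arranges specialist follow-up.

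**The concern.** The planned summary does not match the question. A median describes a typical encounter. A service planner needs the time consumed by a given number of encounters, which is the number times the mean. The two agree only where mean and median coincide, as in a symmetric distribution.

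The design gives two reasons to expect a gap.

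- Informing time is sampled, so its total cannot be found by adding up and has to be extrapolated. The median does not extrapolate to a total.
- Notification work combines many short negative contacts with a few long positive ones. If the two are pooled, the median is in effect that of the negatives and says almost nothing about the work on positives.

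At stake is whether the reported figures can support the staffing side of objective 6. A reader who multiplied them up would arrive at too few hours.

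**Working it through.** The plan states no figure for staff time or workload, so there is none to reproduce. The check shows how far volume × median falls short of volume × mean under stated assumptions.

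**Inputs from the protocol**
- Study size: 4,000 (Sample size).
- New-diagnosis rates: 1/1000 for HIV and 1/100 for HCV (Hypothesis). Together 0.001 + 0.010 = 0.011, or 1.1% of patients, ignoring coinfection.

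**Assumed, because the protocol gives nothing**
- The shape and spread of the times.
- A median of 2 minutes for informing a patient.
- 5 minutes per negative result, and 30, 60 or 120 minutes per positive.

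**Check 1: skewed times in one group.** For a log-normal distribution with log-SD s, mean/median = exp(s²/2). The proportion of total time missed by volume × median is 1 − exp(−s²/2). The median-based total is 4,000 × 2 / 60 = 133 hours.

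| s | mean/median | understatement | hours from the mean |
|---|---|---|---|
| 0.25 | 1.03 | 3% | 138 |
| 0.50 | 1.13 | 12% | 151 |
| 0.75 | 1.32 | 25% | 177 |
| 1.00 | 1.65 | 39% | 220 |
| 1.25 | 2.18 | 54% | 291 |

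With s = 0 the two totals agree, so the whole effect comes from skewness.

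**Check 2: negative and positive results pooled.** With 98.9% of results negative, the pooled median is 5 minutes whatever a positive takes. The mean is 0.989 × 5 + 0.011 × t, where t is the time per positive.

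| t (min) | mean (min) | mean above median | median below mean |
|---|---|---|---|
| 30 | 4.945 + 0.330 = 5.275 | 5.5% | 1 − 5/5.275 = 5% |
| 60 | 4.945 + 0.660 = 5.605 | 12% | 1 − 5/5.605 = 11% |
| 120 | 4.945 + 1.320 = 6.265 | 25% | 1 − 5/6.265 = 20% |

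The last column is on the same base as the understatement in Check 1. The result depends on the positive rate. At t = 120 the mean exceeds the median by 2.3% if 0.1% are positive and by 46% if 2% are. The mixture takes no account of variation within each group, which would widen the gap if right-skewed.

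**The case against.** The strongest reply is that the plan never takes the harmful step. A reader might infer that the trial will under-resource the service, or that programme cost will come out too low because it is built on medians. The documents support neither inference. Nothing says a median will be multiplied by volume, cost has its own sentence, and the only named cost source is for tests. The missing rule for valuing staff time is a separate gap, which adding a mean would not close by itself.

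Other points also stand.

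- Objective 6 does not use the words total workload. Reading it as a question about total time is an inference, though a fair one for services needed to continue a programme.
- Medians are a conventional summary of skewed times and suit the description of a single encounter.
- Individual notification times will be recorded, so a mean or sum remains obtainable.
- The Analyses section does not say that negative and positive results will be pooled. Check 2 applies only if they are.
- Work on positives is shared between investigator and nurse, so it is not all nursing time.
- With little skewness the gap is small: 3% at a log-SD of 0.25.

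These points limit the claimed harm but do not remove the mismatch. The stated objective concerns resources for a volume of tests, and the only planned time summary cannot be scaled to a volume.

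**Conclusion.** The point holds in conditional form. For the time to inform patients and the time to announce results, the plan offers only medians, while secondary objective 6 calls for a summary that scales with volume. If the service were sized from those medians, workload would be understated when times are right-skewed: by 3% to 54% for log-normal times with log-SD 0.25 to 1.25, and by 5% to 20% in the pooled mixture with 1.1% positives. All these percentages rest on assumed distributions, because the protocol gives none. They are illustrations, not predictions for this emergency department.

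The matter is confined to a descriptive secondary outcome. The prevalence estimates, the sample size and the care-cascade proportions are untouched. It is a worthwhile improvement at almost no cost, not a flaw that threatens the study.

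**What to change.** Keep the medians as description and add the following to the Analyses section.

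1. For each time component, report the arithmetic mean with a bootstrap 95% confidence interval.
2. Report results-management times separately for negative and positive results, and keep nurse and physician time apart where both are recorded.
3. Estimate total informing time as the sample mean times the number of patients approached.
4. Report total results-management time as the sum of recorded times, or as mean times volume within each result group.
5. If programme cost includes staff time, base that element on these totals and state the unit cost used.

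Items 1 to 4 use times the protocol already plans to record and take a few lines of analysis. Item 5 needs a unit cost for staff time, which the protocol does not name, if staff time is to be costed.
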